10 ANALYSIS POPULATIONS

The main population for non-safety analysis will be the full analysis set (FAS). In addition, a sensitivity analysis using the PP Population will be performed for every non-safety objective. This will be done if the FAS is not equal to the PP Population.

Safety data will be analyzed using the Safety Population.

10.1 Screened Population

The screened population consists of all subjects who gave informed consent.

10.2 Randomized Population

The randomized population consists of all subjects who were randomized.

10.3 Full Analysis Set

The FAS consists of all the randomized subjects who had at least one post-randomization product use experience and have at least one valid non-safety assessment.

10.4 Per Protocol Population

The PP population is a subset of the FAS and includes all randomized subjects who have no major protocol deviations impacting evaluability as defined **Table 14** (see Section 11“Protocol Deviations”).

10.5 Safety Population

The Safety Population consists of all the subjects who had at least one exposure to CHTP1.0 (product test at Admission Day). Subjects in the Safety Population will be analyzed according to actual exposure.

11 PROTOCOL DEVIATIONS

Protocol deviations are defined as deviations from the study procedures, including but not limited to any violation of inclusion/exclusion criteria, assessments not performed or performed outside the scheduled time windows, or use of drugs that are known to affect study endpoints.

All protocol deviations will be entered into the clinical trial management system (CTMS) or other approved format.

All deviations will be reviewed and each deviation will be classified as major or minor; all major deviations will be further reviewed to determine whether or not the deviation impacts the evaluability of the results and therefore should result in the subject being excluded from the PP Population.

11.1 Major Protocol Deviations

Subjects with major protocol deviations will be identified (at a population level) to determine whether they will be excluded from any analysis population. This will take place during the pre-analysis data review meeting prior to database lock. The following have been identified as the major protocol deviations.

The categories for the major deviations may include, but are not limited to the deviations presented in **Table 14**.

**Table 14: Definition of Major Protocol Deviations**

Category	Description
Mis-randomization	An error in the randomization and/or product allocation process including being administered the wrong product according to the randomization schedule.
Product compliance	Use of any nicotine or tobacco-containing product other than the assigned product.
Protocol violation	A deviation to the inclusion/exclusion criteria.
Procedural violation	A deviation in the conduct of a procedure
Violation of 24 hour urine collection	Not all urine collected over 24 hours or collection period does not cover 24h +/- 30 min
Concomitant medication	Use of drugs which are known to affect CYP2A6 activity.

Subjects with violations of inclusion criteria 1, 2, 4 and 6, or of exclusion criteria 2 to 4, 10, 16, 19 and 20 will be excluded from the PP Population. Other violations of the inclusion and exclusion criteria will be reviewed for their impact on the evaluability of the primary objectives during the pre-analysis data review meeting (Section 10.4 “Per Protocol Population”).

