7.6.2 Urine Samples

Spot urine samples will be used for the urine drug screening, urine cotinine test, urine pregnancy test and safety urine analysis.

Twenty four-hour urine will be collected from Day -2 to Day 6 on site to measure BoExp. On Day 1, product use must not start prior to the end of urine collection of Day -1.

Twenty four-hour urine sample collection for Day -2 will start approx. at 06:30 AM on Day -2 after the first morning void which should be discarded and will end after 24 hours \pm 1 hour on Day -1

From Day -1 on, the 24-hour urine collection for the respective day will immediately start after the end of 24-hour urine collection of the previous day (after 24 hours \pm 1 hour) (Appendix A). After nearly 24-hours of urine collection, subjects will empty their bladder again and this urine will be used as the final portion of the 24-hour urine sample. During the collection period, all urine passed must be collected and put into the sampling container, with the exception of about 10 mL for the spot urine tests (described above). The spot urine sample of the amount of 10 mL for the urine pregnancy test and safety urine analysis will be taken from the final portion of the 24-hour urine sample before putting this final portion into the sampling container. The amount of 10 mL for the spot urine tests should not be subtracted from the 24-hour urine

Confidentiality Statement

Data and information contained in this document are considered to constitute trade secrets and confidential commercial information, and the legal protections provided to such trade secrets and confidential information are hereby claimed under the provisions of applicable law. No part of this document may be publicly disclosed without the written consent of Philip Morris Products S.A.

sample. No urine must be passed into the toilet. The start and the end time of urine collection will be recorded by the subject in a form and checked by the site collaborators. The volume of 24-hour urine will be measured by the site collaborators upon collection of urine containers from the subjects.

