9 STUDY ACTIVITIES

A detailed schedule of assessments can be found in [Appendix A](#).

The time points shown are to be considered the time of assessment for the first subject. As not all subjects can be treated at the same time, a short time window will be implemented for subsequent subjects. Measurements not conducted at the exact time point, but conducted within the given time window (if applicable) do not constitute a protocol deviation but an accepted variability for the given time point.

In general, if no start time for the procedure is provided, then the procedure can be performed at any time during the day.

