Start of Procedure		Day 6	
		AE/SAE recording	At any time of the day
		Concomitant medications	At any time of the day
		End of 24-hour urine sample collection for Day 5	The urine is collected for 24 hours \pm 1 hour.
		Urine sample to be taken from the 24-hour urine of Day 5	Aliquots from 24-hour urine will be collected according to Table A2. Bio-banking for biomarkers (if additional consent is obtained)
06:29 AM \pm 30 min	√	Clinical laboratory parameters (hematology, clinical chemistry)	After at least 10 hours of fasting
06:29 AM \pm 30 min	√	CYP2A6 activity in plasma	Has to be done before smoking
Before Discharge		Spirometry pre- and post-bronchodilator (recording of FEV ₁ , FVC, FEV ₁ /FVC)	Has to be done before smoking At rest in sitting position for at least 15 minutes prior to pulmonary function testing In sitting position All post-bronchodilator spirometry testing will be performed 15-30 minutes post administration of salbutamol
06:29 AM \pm 1 hour		MNWS questionnaire	
06:29 AM \pm 1 hour		Assessment of cough (VAS)	

Confidentiality Statement

Data and information contained in this document are considered to constitute trade secrets and confidential commercial information, and the legal protections provided to such trade secrets and confidential information are hereby claimed under the provisions of applicable law. No part of this document may be publicly disclosed without the written consent of Philip Morris Products S.A.

Time	Blood Sample	Procedures	Additional Information
Start of Procedure		Day 6	
Prior to 11:30 AM	√	Bio-banking for biomarkers, transcriptomics and lipidomics	If additional consent is signed After at least 10 hours of fasting
Before Discharge		Vital signs (blood pressure, pulse rate, respiratory rate)	At least 5 minutes in supine position
Before Discharge		Physical examination, body weight, and calculated BMI	
Before Discharge		Safety urine analysis	
Before Discharge		Urine pregnancy test (females only)	
Before Discharge		ECG	At least 10 minutes in supine position prior to recording
Before Discharge		Information on the risks of smoking, smoking cessation advice and debriefing.	
		Discharge	

Abbreviations: AE = Adverse event; BMI = Body mass index; BoExp = Biomarker (s) of exposure; CC = Conventional cigarette(s); CYP2A6 = Cytochrome P450 2A6; FEV₁ = Forced expiratory volume in 1 second; FVC = Forced vital capacity; MNWS = Minnesota nicotine withdrawal scale (revised version); SAE = Serious adverse event

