11.1.2 Protocol Deviations

Protocol deviations are defined as deviations from the study procedures as defined in this document, including but not limited to any violation of inclusion/exclusion criteria, assessments not performed or performed outside the scheduled time windows, or use of drugs that are known to affect study endpoints.

All protocol deviations will be entered into the clinical trial management system (CTMS) or other approved format.

Information from the source documents will represent the primary source of protocol deviations. Information following site monitoring and other manual reviews will be documented in the site visit reports, follow-up letters, audit documentation, or other manual review and will be recorded and tracked in the CTMS or other approved format. Telecommunications and other verbal communications regarding deviations will be considered

Confidentiality Statement

Data and information contained in this document are considered to constitute trade secrets and confidential commercial information, and the legal protections provided to such trade secrets and confidential information are hereby claimed under the provisions of applicable law. No part of this document may be publicly disclosed without the written consent of Philip Morris Products S.A.

and handled as important communication, documented and tracked as protocol deviations, as necessary.

Individual entries for protocol deviations that are recorded in the CTMS, or other approved format, following site monitoring and other manual reviews will be reviewed against the individual data points in the CRF database but will not be formally reconciled with the CRF database (e.g., their description or occurrence date). The overall procedure for managing protocol deviations is described in the SOPs and/or agreed upon procedure of the CRO data management team. All deviations will be reviewed periodically, as determined at study start, to identify trends to improve monitoring and/or potential impact on the statistical analysis.

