12.3.2 Per Protocol Population

The PP population is a subset of FAS and includes all randomized subjects who fulfill key compliance criteria of the protocol, and have no major protocol deviation (to be further described in the SAP).

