11.3 Assessment Windows

Smoking of the randomized products should take place within the 06:30 AM and 11:00 PM window.

The assessment windows are shown in **Table 16**.

Table 16: Assessment Windows

Assessment	Nominal Time point(s)	Window
24 h urine sample	Start (All days)	06:30 AM \pm 1 hour
	End on the following day (All days)	06:29 AM \pm 1 hour
CYP1A2 activity in plasma	Start (Days -1 and 5)	6 hours after intake of cup of coffee \pm 15 min
CYP2A6 activity	Day -1 and Day 6	Prior to smoking / product use
CO breath test	Day -2 to Day 5	In the evening prior to 09:00PM (approx 08:00 PM \pm 1 hour)
Assessment of Cough	Day -1 to 5	To be done prior to product use but not later than 11:30 AM
	Day 6	06:29 AM \pm 1 hour
MNWS questionnaire	Day -1 to 5	To be done prior to product use but not later than 11:30 AM
	Day 6	06:29 AM \pm 1 hour
QSU-brief questionnaire	Day -2 to 5	08:00 PM to 11:00 PM
MCEQ questionnaire	Day -2 to 5	08:00 PM to 11:00 PM
Nicotine and cotinine in plasma	Day -2 to Day 5	In the evening prior to 09:00PM (approx 08:00 PM \pm 1 hour)

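### SAP Table 14 makes a 24-hour urine collection outside 24 h ± 30 min a major protocol deviation, although the protocol allows 24 h ± 1 h and does not treat in-window measurements as deviations

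*SAP*

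**What the plan says.** **Protocol.** Section 7.6.2 says that the first collection, for Day -2, "will end after 24 hours \pm 1 hour on Day -1", and gives the same tolerance for the later days. The daily schedule tables in Section 9.2 repeat it: "The urine is collected for 24 hours \pm 1 hour". This includes Table 15, which covers the end of the Day 5 collection that carries the three urinary primary endpoints. The introduction to Section 9 says that measurements taken off the exact time but within the given window "do not constitute a protocol deviation but an accepted variability for the given time point". Section 11.1.2 counts as timing deviations "assessments not performed or performed outside the scheduled time windows". Section 12.3.2 leaves the description of major deviations to the SAP.

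**SAP.** Section 11 repeats the protocol's definition of a deviation. Table 14 in Section 11.1 then lists as major: "Not all urine collected over 24 hours or collection period does not cover 24h +/- 30 min". Table 16 in Section 11.3 gives clock windows of 06:30 AM ± 1 h for the start of a collection and 06:29 AM ± 1 h for its end on the following day. Section 10.4 ties the PP population to Table 14: it "includes all randomized subjects who have no major protocol deviations impacting evaluability as defined" in that table.

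**The concern.** The SAP halves a tolerance that the protocol states many times, and it calls the result a major deviation from that same protocol. A site that follows the protocol exactly can generate major deviations. The revision note for SAP version 2.0 mentions a clarification of the deviation section and a correction of the Section 11.3 windows to match the protocol, but neither remark explains the 30 minutes. SAP Section 9, which lists changes from the protocol down to a change of preposition in the creatinine wording, does not mention it.

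Two outputs are exposed:

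- **Deviation summary (SAP Section 12.2).** It counts subjects with major and minor deviations by product, and would include compliant subjects among the major ones.
- **PP population.** Every major deviation is reviewed for exclusion. The protocol planned PP analyses for the primary endpoints only, and only if more than 20% of subjects were excluded. SAP Section 9 extends them to every non-safety objective whenever the FAS and PP populations differ, so membership matters more than it did in the protocol.

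**Working it through.** The plan states no figure to reproduce on this point. The check sets the windows side by side.

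**Permitted durations**

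| Source | Rule | Range | Width |
|---|---|---|---|
| Protocol 7.6.2 and schedule tables | 24 h ± 1 h | 1380–1500 min (23.0–25.0 h) | 120 min |
| SAP Table 14 | 24 h ± 30 min | 1410–1470 min (23.5–24.5 h) | 60 min |

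The difference is 120 − 60 = 60 min, namely 23.0–23.5 h and 24.5–25.0 h. This is half of the protocol window. It is not a share of subjects.

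**SAP Table 16.** The nominal interval from 06:30 AM to 06:29 AM the next day is 1439 min. If start and end vary independently by ± 60 min, durations can run from 1439 − 120 = 1319 min (21.98 h) to 1439 + 120 = 1559 min (25.98 h). The clock windows alone therefore do not enforce the protocol's 23–25 h, and Table 14 holds the only limit on duration in the SAP.

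**Example 1.** A collection from 06:45 AM to 06:00 AM the next day lasts 23 h 15 min, which is 45 min short of 24 h. It is inside the protocol's ± 60 min. Its start is inside 05:30–07:30 AM and its end inside 05:29–07:29 AM, so both Table 16 windows are met. It is a major deviation under Table 14.

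**Example 2.** Each subject has seven consecutive collections, and each starts when the previous one ends (protocol 7.6.2 and Table A2). One final void at 07:10 AM between two at 06:30 AM gives durations of 24 h 40 min and 23 h 20 min. Both satisfy the protocol and both are major under Table 14, which is not restricted to baseline or Day 5.

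**Effect of duration on the endpoints.** SAP Section 7.1.1 defines quantity excreted as concentration times urine volume, with no correction for duration. Assuming a constant excretion rate:

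- shift at 30 min: 0.5/24 = 2.1%; at 1 h: 1/24 = 4.2%
- longest-to-shortest ratio: 24.5/23.5 = 1.043 under ± 30 min; 25/23 = 1.087 under ± 1 h

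The urinary primary endpoints are biomarker concentrations divided by creatinine from the same collection, so duration should have little direct effect on them. COHb is measured in blood.

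**The case against.** **The SAP was given this choice.** Protocol Section 12.3.2 leaves major deviations to the SAP, and because the Table 16 windows alone would allow about 22 to 26 h, a separate duration limit is needed. This stands: the SAP may set an evaluability limit, and failing Table 14 while meeting Table 16 is failing a different test. But a major deviation is a grade of protocol deviation. The power to grade deviations does not turn a collection that the protocol calls compliant into one.

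**In-window collections might never be logged.** SAP Section 11 first identifies a deviation and then classifies it, so Table 14 might have nothing to act on. That reading is possible. However, Section 11.1 presents the Table 14 items as the identified major deviations, and someone applying the table would flag these collections. The text supports both outcomes, which is itself a reason to reconcile it.

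**Protocol Section 9 concerns clock scheduling.** Its rule is explained by the fact that subjects cannot all be processed at once. Applying it to duration is an inference, but a natural one, because the schedule tables state the collection window as a duration.

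**The practical effect is small.** The FAS primary analysis is untouched, PP exclusion follows only after review, and PP is a sensitivity set. Protocol 7.6.2 also has subjects void shortly before 06:29 AM on Day 6, which makes large departures less likely for the Day 5 sample. All of this stands and limits the consequence, but it does not remove the contradiction.

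**Conclusion.** The concern holds. Collections of 23.0–23.5 h and 24.5–25.0 h comply with the protocol and are major deviations under SAP Table 14, and neither document gives a reason. The mismatch rests on explicit text and simple arithmetic.

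Its consequence is limited to the deviation summary by product and, after review, to PP membership. The number of subjects concerned is unknown. The 2.1% and 4.2% shifts in quantity excreted assume a constant excretion rate. The primary inference is not affected. The point should be corrected because the SAP uses this threshold to classify subjects, and the two documents currently give the data review meeting contradictory limits.

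**What to change.** Before database lock, do one of the following:

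1. **Align.** Replace the 30-minute tolerance in SAP Table 14 with the protocol's 24 h ± 1 h, applied together with the Table 16 clock windows. The accepted range widens from 60 to 120 minutes and matches the protocol.
2. **Declare.** If a tighter limit is wanted, for instance to protect the quantity-excreted analyses, state it with its reason in SAP Section 9 as a PP evaluability criterion. Do not report in-window collections as protocol deviations.

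The cost is one table cell or one entry in Section 9. The downside of the first option is that collections 30 to 60 minutes off 24 h stay in the PP analyses of quantity excreted, with a shift of about 2 to 4% under a constant excretion rate.

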11.2 Minor Protocol Deviations

The categories for the minor deviations may include, but are not limited to the deviations presented in **Table 15**.

Table 15: Definition of Minor Protocol Deviation Categories

Category	Description
Time deviation (Questionnaires)	Assessments not taken at the correct time or within the allowed time window (see Table 16)
Time deviation (Blood draws)	Assessments not taken at the correct time or within the allowed time window (see Table 16)
Time deviation (CYP1A2 activity)	Assessments not taken at the correct time or within the allowed time window (see Table 16)
Time deviation (CYP2A6 activity)	Assessments not taken at the correct time or within the allowed time window (see Table 16)
Time deviation (Assessment of cough)	Assessments not taken at the correct time or within the allowed time window (see Table 16)
Time deviation (CO breath test)	Assessments not taken at the correct time or within the allowed time window (see Table 16)
Visit window deviation	Assessments not taken at the correct time or within the allowed time window (see Table 16)

**Table 15: Definition of Minor Protocol Deviation Categories**

Category	Description
Time missing	Assessment date or time is missing
Procedural violation	A deviation in the conduct of a procedure
Assessment missing	Assessment is missing
Visit missing	Scheduled visit not done

11.3 Assessment Windows

Smoking of the randomized products should take place within the 06:30 AM and 11:00 PM window.

The assessment windows are shown in **Table 16**.

Table 16: Assessment Windows

Assessment	Nominal Time point(s)	Window
24 h urine sample	Start (All days)	06:30 AM \pm 1 hour
	End on the following day (All days)	06:29 AM \pm 1 hour
CYP1A2 activity in plasma	Start (Days -1 and 5)	6 hours after intake of cup of coffee \pm 15 min
CYP2A6 activity	Day -1 and Day 6	Prior to smoking / product use
CO breath test	Day -2 to Day 5	In the evening prior to 09:00PM (approx 08:00 PM \pm 1 hour)
Assessment of Cough	Day -1 to 5	To be done prior to product use but not later than 11:30 AM
	Day 6	06:29 AM \pm 1 hour
MNWS questionnaire	Day -1 to 5	To be done prior to product use but not later than 11:30 AM
	Day 6	06:29 AM \pm 1 hour
QSU-brief questionnaire	Day -2 to 5	08:00 PM to 11:00 PM
MCEQ questionnaire	Day -2 to 5	08:00 PM to 11:00 PM
Nicotine and cotinine in plasma	Day -2 to Day 5	In the evening prior to 09:00PM (approx 08:00 PM \pm 1 hour)

**Table 16: Assessment Windows**

Assessment	Nominal Time point(s)	Window
COHb blood sampling	Day -2 to Day 5	In the evening prior to 09:00PM (approx 08:00 PM \pm 1 hour)
HPT Questionnaire	Day -2, Day 1 and Day 4	08:00 PM-11:00 PM
HPT Recording	Day -2, Day 1 and Day 4	for all smoking events when compatible CCs are smoked

12 Planned Statistical Methods

12.1 General Considerations

Data analysis will be performed using SAS[®] Version 9.2 or higher.

Data listings will be provided for all data collected as required by this protocol, ordered by product arm and subject and time point (if applicable), unless otherwise stated. Summary statistics and statistical analysis will only be presented for data where detailed in this SAP. All unscheduled assessments will be included in the listings.

Safety data will be summarized for the Safety Population.

12.1.1 Stratified Presentation

For the analysis and descriptive statistics of the primary study endpoints, the following stratification criteria will be used:

1. Sex (male; female).
2. Average daily CC consumption over the 6 weeks prior to admission as reported on the Admission Day (smokers smoking 10 to 19 CC/day and smokers smoking > 19 CC/day).

12.1.2 Subgroup Analyses

No subgroup analyses will be performed in this study.

12.1.3 Descriptive Statistics

For continuous data, summary statistics will include the number of subjects (n), the number and percent of subjects with missing data, the arithmetic mean, arithmetic SD, median, first and third quartiles, minimum, maximum, and number; for log-normal data the geometric mean and geometric CV will also be presented. For categorical data, frequency counts and percentages will be presented. Data listings will include all subject level data collected unless otherwise specified. Summary statistics and statistical analyses will generally only be performed for subjects included in the relevant analysis population. For the calculation of summary statistics and statistical analysis, unrounded data will be used.

Summaries on the Safety Population will be produced by actual exposure. Subjects who tested the product but were discontinued before randomization will be shown in a separate column /table.

The following product labels will be used throughout the TFLs (**Table 17**):

Table 17: Product Labels		
Product	Format used in TFLs	Order in TFLs
Carbon Heated Tobacco Product	CHTP	1
Conventional cigarettes	CC	2

The following stratification labels (**Table 18**) for the TFLs will be used:

Table 18: Stratification Labels	
Stratification Factor	Definition
Sex	male
	female
Daily CC consumption (per day)	<10 ¹
	10-19
	>19

¹ Note that due to inclusion criteria for the study there should not be any subjects with daily CC consumption < 10, therefore this category will not be presented unless there is sufficient data for analysis/presentation (see Section 12.1.5.1 "Insufficient Data for Analysis/Presentation").

